#### **4.2b Study personnel**

The intervention will be administered by Health and Care Professions Council (HCPC) registered physiotherapists. Physiotherapists will be provided with information on study

rationale, objectives and intervention in the form of a clinician handbook and will be required to attend either one-to-one or group practical training on administering the exercise intervention.

### **SECTION 4.3 Intervention**

All participants will receive the study intervention in addition to standard management of acute LPD by the trauma and orthopaedic service at the John Radcliffe hospital. Typically, this involves the provision of a lateral buttress splint and referral to physiotherapy with no limitations on weight-bearing or knee range of movement. Patients may receive advice on pain management, gait re-training and instruction of basic knee exercise from a member of the orthopaedic team or physiotherapist working in the NPC. No attempt will be made to modify this but what has been delivered in addition to the study intervention will be recorded in the study treatment logs to help characterise what acute care was delivered overall.

The intervention will be comprised of up to 6, one-to-one, physiotherapy sessions over a maximum duration of 3 months. 1 or 2 more sessions will be allowed only if deemed clinically essential. Additional sessions and the reasons for these will be recorded to understand if the intervention would need adapting for future studies. Less than 6 physiotherapy sessions can be agreed with the participant if they are self-managing effectively and their goals have been achieved, (these stopping rules will be recorded). A treatment duration of up to 3 months is representative of current care in the NHS for first-time LPD. Initial physiotherapy sessions will be 45-60 minutes and subsequent physiotherapy sessions will be 30 minutes as per local practice.

The exercise intervention has been designed to address the biomechanics associated with the LPD mechanism of injury, improve common lower limb strength deficits in this patient population and facilitate a return to the participant's desired activities which may include activities such as running, hopping and twisting.

The LPD mechanism of injury is thought to result from a quadriceps contraction with the knee in a position of slight knee flexion, femoral internal rotation and tibial external rotation which forces the patella laterally. This is supported by studies demonstrating peak lateral displacement of the patella at angles of 0-30° knee flexion in patients with patellofemoral

instability and increased contact pressures on the lateral aspect of the patella with femoral internal rotation and tibial external internal rotation. Movement patterns at the trunk and lower limb known to increase knee abduction loading will also be targeted as increased knee abduction loading at reduced knee flexion angles during sport specific tasks is associated with other common knee injuries such as patellofemoral pain and anterior cruciate ligament injury. Correction of these movement patterns will be achieved by advising participants on correct technique during the performance of their exercise programme and through strengthening of the lower limb muscles that control these movements.

Strengthening exercises will be a core component of the exercise intervention as reduced strength of the hip extensors, abductors and external rotators is associated with greater knee valgus during single leg drops landing, and reduced quadriceps strength is common in patients with a history of LPD and a risk factor for the development of patellofemoral osteoarthritis.

To ensure the intervention is standardised, exercises prescribed to participants will be from a pre-determined list of exercises categorised into range of movement, strength and neuromotor exercises of progressive difficulty. Physiotherapists will also have the option of choosing one exercise not on this list if they feel it is necessary for the participant's rehabilitation. This will be recorded in the study treatment logs. Exercises will be selected based on the physiotherapist's assessment, and the participant's preferences and activity related goals.

To ensure progressive improvements in muscle strength, the prescribed dose of strengthening exercises will be in line with current guidelines. There is currently a lack of evidence to inform the most effective dose for exercises that incorporate sport specific and functional tasks such as agility, hopping and balance. Therefore, the dose of these exercises prescribed will be at the discretion of the physiotherapist and noted in the study treatment log. Patients will be required to perform the exercise programme independently a minimum of three times per week on non-consecutive days as recommended. Initially when pain may limit participants attaining the prescribed exercise intensity for strengthening exercise, participants can perform their exercises more frequently if they find this beneficial.

The intervention will also incorporate simple behaviour change techniques known to increase participant adherence to exercise. These will include goal setting, provision of written instruction, and demonstration and participant practice of the selected exercises.  
 Guidance and recommendations on how to implement these strategies into practice have been developed and have informed the design of our intervention.

At the initial assessment, participants will be required to select an activity related long-term goal. Short-term goals to be achieved by the next treatment session will be selected at all subsequent appointments except the last one. Participants will be facilitated in setting appropriate goals by their physiotherapist using recommended guidelines.

Written information will be provided in the form of a participant information booklet. This will contain information about the nature of their injury, self-management and guidance on the exercises to be completed. Rationale for the intervention and proposed benefits associated with this will be re-emphasised throughout the intervention.

Physiotherapists will demonstrate the selected exercises followed by participants. Feedback will be provided, and participants will be asked if they would like to be recorded performing the exercises on their smartphone to increase technique compliance. The patient will be asked about their intention to adhere. If the intention is low, the barriers to adherence will be elicited and strategies to overcome them will be explored (following the principals of patient centred goal setting).

Participants will be provided with, and asked to complete, an exercise diary containing their exercises and guidance on achieving an effective dose. At the end of each session participants will be encouraged to ask questions, their understanding will be assessed and any clarifications needed will be provided. At each review session participant adherence and achievement of short-term goals will be reviewed and strategies to overcome any barriers will be explored

#### **4.3a Intervention – modifications**

In the event of increased pain or swelling while completing the exercise intervention participants will, where possible, be advised to complete less repetitions or sets while remaining within the prescribed set and repetition range of the exercise identified as provoking their symptoms, or to regress to the previous level of this exercise, until

symptoms are at a level the participant is happy to continue to exercise with. If a specific exercise cannot be identified as the cause of the symptoms, all exercises will be reduced to a level, or set and repetition range, the patient is happy to continue to exercise with. If it is not possible to continue exercising for that exercise session, advice about application of ice, analgesia and relative rest will be provided where necessary and the patient will be reviewed at the next exercise session.

#### **4.3b Intervention – concomitant care**

As the efficacy of the intervention is not in question, concomitant health care such as medication use will not be recorded, and other aspects of care will continue as usual.

### **SECTION 4.4 Outcomes**

#### **4.4a Primary outcomes**

- Eligibility defined as the % of participants with a diagnosis of LPD, screened for eligibility, who satisfy the eligibility criteria
- Recruitment rates defined as the % of eligible participants who consent to participate in the study
- Acceptability defined as the % attrition rate (participants who fail to complete follow up data collection at 3 months) and participant response to a patient satisfaction questionnaire
- Adherence defined as the % of scheduled physiotherapy sessions attended and participant self-reported intervention adherence defined as the % of prescribed exercise sessions completed

#### **4.4b Secondary outcomes**

- Acceptability of outcome data collection by participants defined as the % completion of the PROMs outlined below.
- The Tegner Activity Scale measures activity on a scale from 0-10, with higher scores indicating higher activity. It has shown good reliability and content validity in patients with acute patellar dislocation and prior dislocation/subluxation and shown to measure a distinct aspect of recovery demonstrated by its low correlation with knee specific and general health questionnaires in this cohort. It has previously been used to assess the effect of conservative management in patients with first

time LPD patients. It will be completed after informed consent has been obtained prior to the first physiotherapy session based on **pre-injury** activity levels and at 3 months after the first physiotherapy session based on their activity levels at that time. It will be administered as a patient completed questionnaire. The change in Tegner Activity Scale scores will be used for analysis.

[figure not shown]
- The Lysholm Knee Scoring Scale was originally developed for patients with knee ligament injuries and subsequently revised. It is scored from 0-100 with lower scores indicating higher pain and disability. It has since demonstrated good test-retest reliability in patients with first time LPD and prior subluxation/dislocation and was able to discriminate between those who subsequently developed recurrent instability and those who did not. It has been used to assess the effect of conservative management in patients with first time LPD and recurrent LPD. It will be completed after informed consent has been obtained prior to the first physiotherapy session and 3 months after the first physiotherapy session based on **current** knee symptoms at that time. It will be administered as a patient completed questionnaire. The change in Lysholm Knee scores will be used for analysis.
- The EQ-5D is a commonly used quality of life questionnaire. It will be completed after informed consent has been obtained prior to the first physiotherapy session and 3 months after the first physiotherapy session based on **current** symptoms at that time. It will be administered as a patient completed questionnaire. The change in EQ-5D scores will be used for analysis.
- Harms. For this study harms will be defined as any unfavourable sign or symptom related to completing the study intervention. The recording of harms has been recommended in feasibility studies to inform future research design and processes. This will be measured from commencement of the intervention to 3 month follow-up as outlined in section 6.2a.
- Determine what assessment findings are consistent with a diagnosis of LPD. A member of the trauma and orthopaedic team will be required to assess the presence/absence of proposed assessment findings to include in the eligibility criteria for future studies as outlined in section 5.1. This will inform the feasibility of using these assessment findings in the eligibility criteria for future studies.

- Intervention delivery. Treatment logs will be analysed to record the duration from injury to commencing the intervention, the number of physiotherapy sessions received by participants, the duration of intervention and the exercises prescribed.

Additional demographic data will be collected as part of the study. Further information on this and the time points for data collection are outlined in section 5.1

### SECTION 4.5 Participant timeline

Participant time line schematic diagram

## **SECTION 4.6 Sample size**

### **4.6a Target sample size**

Data we collected from the John Radcliffe trauma service for 2017 conservatively estimates 31 LPD patients match our eligibility criteria and 51 LPD patients are of unknown eligibility, due to the required information not being available in the patient's medical records. Of those of unknown eligibility, 23 are due to the direction of dislocation not being reported. As medial patellar dislocations are exceedingly rare a conservative estimate would be 54 eligible participants per year and 27 for our planned recruitment period of 6 months.

We aim to recruit 15 participants over 6 months. Recruitment will cease at the end of the designated recruitment period of 6 months or earlier if the target of 15 participants is achieved.

Previous trials in the UK investigating conservative interventions for this condition have reported low recruitment rates but not explicitly stated what these rates were. This makes it difficult to estimate recruitment rates for this study and why it forms one of our primary objectives. We feel a recruitment target of 15 participants is feasible due to our conservative estimate of eligible participants and the broader inclusion criteria in our study compared to previous studies.

As this is a feasibility study, no power calculation has been performed. A sample size of 15 is a pragmatic choice. This has been used for a study similar to ours, a single group prospective study investigating the acceptability and feasibility of exercise for patients with endometrial cancer.

## **SECTION 4.7 Recruitment**

### **4.7a Screening and eligibility assessment**

Clinic lists for the trauma and orthopaedic NPC will be screened for patients with a knee injury. Patients will be assessed by a member of the trauma and orthopaedic team as per their usual practice. Patients subsequently diagnosed with a LPD will be assessed to see if they meet the study eligibility criteria (as described in section 4.2a). Eligible participants will be provided with the participation information sheet and asked if they wish to participate in the study.

Referrals to the trauma outpatient physiotherapy department at the John Radcliffe hospital will also be screened to identify additional potential participants (e.g. patients referred to physiotherapy directly from the Emergency Department (ED) and not seen in the trauma and orthopaedic NPC). Information packs, containing an invitation letter and participation information sheet, will be sent to potential participants with *CF*'s email address and phone number. The invitation letter and participant information sheet will advise that consent to participate in the study is strictly voluntary, ongoing and can be withdrawn at any time (as described in section 7.3). Patients interested in participating in the study will register their interest by telephone or email. An initial consultation to review eligibility criteria and obtain informed consent will be arranged at the time of their first physiotherapy appointment to limit participant inconvenience.

Eligible patients who decline to participate will have their age and gender recorded. They will also be asked their reasons for declining to participate, and if given, these will also be recorded. This will allow us to compare the characteristics of those recruited and those who chose not to participate. Those who do not meet the eligibility criteria or who decline to participate will be referred to their local physiotherapy provider (including the John Radcliffe trauma outpatient department where appropriate) as they normally would.

Informed consent for eligible participants who wish to participate in the study will be obtained as outlined in section 7.3.

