## **SECTION 5 METHODS: DATA COLLECTION, MANAGEMENT, AND ANALYSIS**

### **SECTION 5.1 Data collection methods**

#### **5.1a Outcomes and time points at which they will be assessed**

Outcome	Measurement	Time point
Demographics	Age, sex, height, weight, affected knee, mechanism of injury (traumatic/atraumatic), previous history of ipsilateral patella dislocation, previous history of contralateral patella dislocation,	Baseline

	time from injury to presentation to acute care (ED or trauma services), family history of patella dislocation, employment status, level of education, ethnicity	
Assessment findings	
Presence/absence of the following on:
 
 
• A convincing patient history of a visible deformity on the lateral aspect of the knee or a sensation of the patella ‘popping’ out of joint followed by spontaneous reduction
 
• Presence of a haemarthrosis or joint effusion on clinical examination
 
• Tenderness along the medial patellofemoral complex (tenderness at the following bony landmarks or at any point extending between these two points: at or just proximal to the medial epicondyle of the femur and the midpoint of the medial aspect of the patella extending to the junction of the medial quadriceps tendon and the patella)
 
• Apprehension on laterally directed force of the patella
 
	Baseline
Eligibility	% of participants with a diagnosis of LPD who meet the eligibility criteria	Completion of study
Recruitment	
% of eligible participants who consent to participate in the study
 
Reasons for not consenting will also attempt to be collected
	Completion of study
Adherence	% of scheduled physiotherapy sessions attended	
Completion of intervention
 
3 months post first

	Participant self-reported % of prescribed home exercise sessions completed	physiotherapy session
Acceptability	% attrition rate  Patient satisfaction questionnaire	Completion of study  3 months post first physiotherapy session
Follow up	% of participants who consent to treatment who return 3 month questionnaires	Completion of study
Knee function, pain and instability	Lysholm Knee Scoring Scale	Baseline, 3 months post first physiotherapy session
Activity level	Tegner Activity Scale	Baseline, 3 months post first physiotherapy session

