### **5.1b Baseline data collection**

All baseline data will be collected after informed consent to participate in the study has been obtained prior to the first physiotherapy session. Participants will be asked to complete a questionnaire at baseline to capture the demographic information and PROMs outlined in section 5.1a. Telephone or email contact will be used to obtain a score, where relevant, if baseline data collection is subsequently identified as being incomplete.

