## **SECTION 5.3 Statistical methods**

### **5.3a Statistical Methods for analysing primary and secondary outcomes**

Statistical methods and results will be reported, where possible, in accordance with SAMPL guidelines. All analyses will be conducted using the latest version of SPSS (IBM Corp. Armonk, NY).

Eligibility, recruitment, acceptability and adherence will be described using descriptive statistics and expressed as integers and percentages where relevant.

Tegner Activity scores will represent ordinal data. Baseline and 3 months post 1st physiotherapy session scores will be described using descriptive statistics using median and inter-quartile range.

Lysholm scores will represent continuous data. Baseline and 3 months post 1st physiotherapy session scores will be described using descriptive statistics using mean and standard deviations if scores are normally distributed or median and inter-quartile range if data is skewed.

EQ-5D-5L scores will represent continuous data. Baseline and 3 months post 1st physiotherapy session scores will be described using descriptive statistics using mean and standard deviations if scores are normally distributed or median and inter-quartile range if data is skewed.

Patient satisfaction scores will be described using descriptive statistics. Ordinal data will be expressed using medians and inter-quartile ranges, and categorical data will be expressed as integers and percentages.

Baseline characteristics and additional outcome data on intervention delivery and harms will be expressed using descriptive statistics. Continuous variables will be described using means and standard deviations for normal distributions or medians and inter-quartiles range for non-normal distributions. Categorical data will be expressed as integers and percentages.

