### **SECTION 7.3 Consent**

Written consent will be obtained in accordance with GCP guidelines and by a researcher identified in the delegation log as being able to take consent. Participants will be informed about the study design, aims of the study and what it will involve for them. Participants will be informed the purpose of the study is not to assess the efficacy of the intervention. Participants will also be provided with written information in the form of a participant information sheet and offered an opportunity to ask questions. Participants will be offered time to consider their participation in the study should they wish to do. Participants will be informed their participation is voluntary and ongoing, and they can withdraw consent at any time with no obligation to explain why and without affecting the quality of their care.

If participants are happy to proceed to enrolment in the study the consent form will be signed and dated by the participant and the researcher. A copy will be provided to the patient, a copy will be placed in the patient's medical notes, and the original kept by the study team.

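### On the referral route consent is taken at the first physiotherapy appointment, so session 1 counts as attended by construction and people who miss it are left out of the primary percentages

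*Combined protocol and SAP*

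**What the plan says.** Section 4.7a describes two ways into the study. Patients diagnosed at the New Patient Clinic are checked against the criteria and approached there: "Eligible participants will be provided with the participation information sheet and asked if they wish to participate in the study". Patients found from physiotherapy referrals are posted a pack and contact the study if interested. For them, "An initial consultation to review eligibility criteria and obtain informed consent will be arranged at the time of their first physiotherapy appointment".

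The text does not fix when a clinic patient signs. Section 7.3 says that "Participants will be offered time to consider their participation in the study should they wish to do". Section 5.1b has one rule for both routes: "All baseline data will be collected after informed consent to participate in the study has been obtained prior to the first physiotherapy session".

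Section 4.4a sets the outcomes: "Adherence defined as the % of scheduled physiotherapy sessions attended", with no exception for session 1; attrition as the percentage of participants without 3-month data; and recruitment as the percentage of eligible people who consent. Section 5.1a counts follow-up as the percentage "of participants who consent to treatment who return 3 month questionnaires", and lists missed appointments for participants only. In section 5.3a, "Eligibility, recruitment, acceptability and adherence will be described using descriptive statistics and expressed as integers and percentages where relevant", with no mention of route.

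Section 4.7a keeps age, gender and any reasons given for eligible people who decline. It has no category for someone who replies to the invitation and then misses the first appointment.

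**The concern.** Attendance, attrition and recruitment are all primary outcomes. On the referral route, turning up to session 1 is a condition of being enrolled, yet that session is then counted as evidence of adherence. The people most likely to show that the intervention or its timing does not suit them, those who agreed to come and did not, leave no trace in any primary figure.

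Section 3.1b gives the reasons for measuring these things: recruitment was difficult in earlier UK trials, and the one earlier trial comparing exercise programmes lost 52% of its participants. A later study that takes consent before the first appointment would meet those non-attenders as participants, and this study's percentages would not have warned of them.

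**Working it through.** **1. The plan's own figure.** Section 4.6a counts 31 patients in 2017 as eligible and adds 23 whose only gap was the direction of dislocation: 31 + 23 = 54 per year, and 54/2 = 27 in six months. Both reproduce. The target of 15 then needs 15/27 = 55.6% to consent. The documents give no expected attendance, attrition, no-show rate or split by route, so the rates in steps 3 to 5 and 7 are assumptions.

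**2. Who is in each denominator.** A referral patient who misses the first appointment cannot have consented at it, so is not a participant. That person is absent from attendance, attrition and the record of missed appointments. Their eligibility was to be reviewed at the same appointment, so they may be absent from the recruitment denominator too.

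**3. The guaranteed session.** Let a course have K sessions and let q be attendance at sessions 2 to K. With session 1 certain, the all-session figure is (1 + (K−1)q)/K, which exceeds q by (1−q)/K. Section 4.3 allows up to 6 sessions and lets fewer be agreed, so K = 3 is shown as a shorter course.

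| q (assumed) | Figure, K = 6 | Lift (points) | Figure, K = 3 | Lift (points) |
|---|---|---|---|---|
| 0.9 | 91.7% | 1.7 | 93.3% | 3.3 |
| 0.8 | 83.3% | 3.3 | 86.7% | 6.7 |
| 0.7 | 75.0% | 5.0 | 80.0% | 10.0 |
| 0.5 | 58.3% | 8.3 | 66.7% | 16.7 |

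For example, (1 + 5 × 0.7)/6 = 4.5/6 = 75.0%.

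**4. The missing no-shows, attendance.** Let d be the share of interested people who miss session 1. Take K = 6 and q = 0.8, so the reported figure is 83.3%.
- If they never attend at all, attendance among everyone interested is (1−d) × 83.3%: 75.0% at d = 10% and 58.3% at d = 30%.
- If they miss session 1 only, it is ((1−d) + 5 × 0.8)/6: 81.7% at d = 10% and 78.3% at d = 30%.

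**5. The missing no-shows, attrition.** Let L1 be loss to 3-month follow-up among session 1 attenders and L0 among non-attenders. Attrition among everyone interested is (1−d)L1 + dL0. With L1 = 20% and d from 10% to 30%:
- L0 = 100%: 28% to 44%.
- L0 = 50%: 23% to 29%.
- L0 = 20%: 20% throughout.

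The reported 20% is too low for that wider group only where L0 exceeds L1.

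**6. Recruitment percentage.** Section 4.6a lists 51 patients of unknown eligibility, of whom 23 were added back in step 1. If all 51 were eligible, the six-month pool would be (31 + 51)/2 = 41, and 15 recruits would be 15/41 = 36.6% rather than 55.6%. These are 2017 counts for the whole trauma service, not the referral route. They only illustrate how far the percentage moves with the handling of unconfirmed eligibility.

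**7. Mixing the two routes.** Let r be the referral share and assume equal course lengths.
- If clinic patients sign before session 1 and attend it at rate q, the pooled lift is r(1−q)/6. At r = 0.5 and q = 0.7 that is 0.5 × 5 = 2.5 points, and it depends on the mix of routes.
- If clinic patients also sign at session 1, the full (1−q)/6 applies to everyone and the mix of routes adds nothing.

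**The case against.** A reader might infer more: that clinic patients consent before session 1, so that pooling the routes biases attendance upward and attrition downward. The text does not support that. Sections 4.7a, 5.1b and 7.3 are all compatible with same-day signing on both routes. The timeline diagram in section 4.5 is not shown in the text available for this review, and it may settle the matter.

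The attrition half is also not automatic. Attrition is defined by missing 3-month data, not by missed sessions, and section 5.1d plans contact with people who do not adhere and does not count as withdrawals those who stop treatment but give data. In the other direction, section 5.1c dates follow-up from session 1, which a non-attender never has. So a lowering is plausible but not shown.

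Three further points stand in part.
- The percentages are correct for the people who enrol; they mislead only if read as applying to everyone who agreed to take part, or to a study that consents earlier.
- The size is modest if later attendance is high, and section 3.2 sets no numerical targets, so no threshold decision turns on it. With 15 participants sampling error is wide: 3/15 (20%) attrition has an exact 95% interval of 4% to 48%. But the effect of the guaranteed session on attendance runs in one direction, and a definition removes it.
- A referral patient who used the time to consider in section 7.3 might sign later, so attendance at session 1 would not be certain for that person. This is a narrow exception.

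**Conclusion.** The point holds for the referral route. Session 1 attendance is built into enrolment there, the attendance definition keeps that session, and interested people who miss it appear in no planned count. The lift over later-session attendance is (1−q)/6 for a 6-session course, between 1.7 and 8.3 points for assumed q from 0.9 to 0.5, and larger for shorter courses. It applies to each participant enrolled in this way; the pooled effect cannot be computed, because the route share and q are not given.

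Lower attrition is possible but conditional on L0 exceeding L1. An extra bias from pooling the routes is not established, because it depends on when clinic patients sign. This is a cheap improvement to how primary outcomes are defined and reported, not a flaw that invalidates them.

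**What to change.** In sections 4.4a and 5.3a:
- Report attendance from session 2 onward for all participants on both routes, beside the all-session figure. The same rule should apply to everyone: dropping only the session at which consent was signed could measure the two routes over different sessions.
- In the recruitment flow, give separate rows for referral patients who were invited, who registered interest, and who then missed the first appointment.
- Give the recruitment percentage with and without people whose eligibility was never confirmed.
- State when clinic-route consent is signed.
- Show the flow counts by route as a descriptive supplement to the pooled figures.

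The cost is a few sentences, three rows and one supplementary table. Session attendance is already recorded for each participant, and no participant procedure changes; the referral rows need only a simple log. The downsides are small counts per route and slightly less favourable attendance and recruitment figures.
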